14.8.2 Dose and treatment schedule

Study treatments in the follow-up phase	Pharmaceutical form and route of administration	Total Monthly Dose	Frequency and/or Regimen	Vials Used
Pasireotide LAR, im	intramuscular (i.m.)	20mg	20 mg q 28 d	1 vial of 20 mg powder, (+1 vial of 2 ml vehicle)
Pasireotide LAR, im	intramuscular (i.m.)	40 mg	40 mg q 28 d	1 vial of 40 mg powder, (+1 vial of 2 ml vehicle)
Pasireotide LAR, im	intramuscular (i.m.)	60 mg	60 mg q 28 d	1 vial of 20 mg + 1 vial of 40 mg or 1 vial of 60 mg powder, (+ 1 vial of 2 ml vehicle)
Pasireotide LAR, im	intramuscular (i.m.)	80 mg	80 mg q 28 d	2 vials of 40 mg powder, (+ 1 vial of 2 ml vehicle)

14.9 Appendix 9: Dose modification information for patients with rare tumors of neuroendocrine origin receiving pasireotide LAR (from protocol SOM230D2203)

For patients who are unable to tolerate the protocol-specified dosing schedule, dose adjustments are permitted in order to keep the patient on study drug.

Study drug for this study will be pasireotide LAR at 60 mg every 28 days. If tolerability issues occur, the treatment dose may be reduced to pasireotide LAR at 40 mg with next scheduled injection. A patient receiving 40 mg showing further tolerability issues may reduce the dose level to 20 mg at the next injection. The investigator may, at his or her discretion, increase the patient's dose of study medication after resolution of tolerability issue. However, patients not able to tolerate the minimum pasireotide LAR dose of 20 mg will be discontinued from study.

Patients who have not achieved symptom control or in whom adequate control is not maintained are permitted to use rescue dose of pasireotide s.c. up to 600 µg b.i.d to control their symptoms at anytime during the study duration. If tolerability issues arise upon use of s.c. injections for rescue purposes, these injections should be stopped. Once the tolerability issue has resolved, the s.c. injections may be resumed if needed. The rescue s.c. dose may not exceed 600 µg b.i.d.

All dose changes must be recorded on the Dosage Administration Record CRF.

Table 14-10 Dose modification for AEs, excluding LFT increase, QT prolongation and hyperglycemia

Adverse event	Action
CTCAE grade ≤ 2	No drug adjustments
CTCAE grade ≥ 3 and assessed as study drug related	
Reduce pasireotide to the next lower dose level.
 
• If the AE improves to grade ≤ 2 before the next administration, increase dose back to the prior dose.• If the dose is increased and the AE recurs at a grade ≥ 3, the dose should be reduced again. The patient should stay on this lower dose and no further dose titrations are allowed.• If the AE does not improve to grade ≤ 2, the dose is to be reduced further. If the AE does not improve to grade ≤ 2 on the minimum study dose, the treatment should be stopped.

For the management of LFT increase, QT prolongation, and hyperglycemia refer to specific instructions provided in [Appendix 2](#), [Appendix 3](#) and [Appendix 4](#).

14.10 Appendix 10: Dose modification information for patients with neuroendocrine tumors receiving pasireotide LAR (from protocol SOM230D2101)

Patients continuing into the roll-over study will receive the same dose of pasireotide LAR every 28 days as the last dose administered during the parent study.

When treatment is interrupted or permanently discontinued due to an AE or abnormal laboratory value the patient must be followed at least once a week for 8 weeks, and subsequently in 4-week intervals, until resolution or stabilization of the event, whichever comes first. If a patient requires a dose delay of > 21 days from the intended day of the scheduled dose, then the patient must be discontinued from the study. However, the patient will be followed up for toxicity as previously described. All patients will be followed for adverse events and serious adverse events for at least 56 days following the last dose of pasireotide LAR treatment.

Table 14-11 outlines the follow-up required for toxicities of specific types and CTCAE grades.

Table 14-11 Follow-up evaluations for selected toxicities

Toxicity	Follow-up evaluation
Hematology	If \geq CTCAE grade 3 neutropenia or \geq CTCAE grade 3 thrombocytopenia have been demonstrated, these parameters must be repeated at least twice a week until resolution to \leq CTCAE grade 1 to allow for initiation of re-treatment, and then at least weekly until either initiation of retreatment or until stabilization.
Renal	If serum creatinine $\geq 2 \times$ ULN has been demonstrated, this parameter must be repeated at least twice a week until resolution to \leq CTCAE grade 1 or baseline to allow for initiation of re-treatment, and then at least weekly until either initiation of re-treatment or until stabilization.
Hepatic	For details on hepatic safety management, please refer to Appendix 2: Hepatic Safety Management
Pancreatic	If amylase and/or lipase \geq CTCAE grade 3 has been demonstrated, these parameters must be assessed once at 2-4 days and once again at 7 days (± 1 day) and be repeated twice a week until resolution to \leq CTCAE grade 2 to allow for initiation of re-treatment, and then at least weekly until either resolution to \leq CTCAE grade 1 or until stabilization. A CT scan or other imaging study to assess the pancreas, liver and gallbladder must be performed within 1 week of the first occurrence of any \geq CTCAE grade 3 of amylase and/or lipase. In patients with serum triglycerides ≥ 500 mg/dL, urine amylase needs to be tested.
Endocrine/metabolic	For details on hyperglycemia management, please refer to Appendix 4: 'Fasting blood glucose management' .
Cardiac	For details on the follow-up and treatment of QT prolongation, please refer to Appendix 3 'Recommended follow up in case of QT-related findings during routine ECG'
Non-laboratory	Patients who experience non-laboratory DLTs must be evaluated at least once a week following demonstration of the toxicity until resolution of the toxicity to allow for re-treatment, until stabilization of the toxicity, or until study completion.

14.10.1 Dose modification and dose delay

The patient should be followed as described in [Table 14-12](#) until the toxicity in question has resolved to CTCAE grade 1 or to the patients' baseline value, or until the toxicity is deemed irreversible.

Patients who cannot be treated with pasireotide LAR within 21 days of the intended dosing day due to drug-related toxicity should have weekly follow-ups that include a physical examination, vital signs including weight, performance status, ECGs, and assessment of adverse events and concomitant medication. Following toxicity, ECG, hematology, renal and liver function tests should be performed as appropriate.

If a patient requires a dose delay of > 21 days from the intended day of the next scheduled dose of pasireotide LAR, then the patient must be discontinued from the study. Patients who discontinue from the study for a study drug-related adverse event or an abnormal laboratory value, must be followed as described in [Table 14-11](#).

For each patient, only one dose reduction will be allowed after which the patient should be discontinued from the study. For each patient, once a dose level reduction has occurred, the dose level may not be re-escalated during subsequent treatment cycles with pasireotide LAR. Dose reduction for pasireotide LAR means treatment at a lower pasireotide LAR dose level. Dose modification for patients treated at the starting dose of 80 mg will be 60 mg.

All interruptions or changes to study drug administration must be recorded on the Dosage and Administration Record eCRF.

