- Uncontrolled diabetes mellitus (DM), consistently high glucose values FPG ≥ 240 mg/dL (13.3 mmol/L) or HbA1c value ≥ 10 % despite appropriate management of diabetes including diet and/or exercise with or without optimal anti-diabetic therapy

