- If FPG > 160 mg/dL or HbA1c >7.5%, despite optimal anti-diabetic therapy, referral to a diabetologist is recommended.
- If grade 3 hyperglycemia (FPG >250 mg/dL; >13.9 mmol/L) at any point in the study, despite appropriate anti-diabetic medication, pasireotide dose should be reduced
- If consistently high glucose values [FPG \geq 240 mg/dL (13.3 mmol/L) or HbA1c \geq 10 %] despite appropriate management of diabetes including diet and/or exercise with or without

optimal anti-diabetic therapy and study drug dose reduction, patient must be discontinued from study treatment as outlined in [Section 7.1.5.1](#). After the last study dose was received, patients have to monitor their fasting blood glucose for 1 month

Figure 14-3 Recommended guidance for fasting self-monitoring blood glucose management

14.5 Appendix 5: Dose modification information for acromegaly or carcinoid patients receiving pasireotide LAR (from protocol CSOM230C2110, CSOM230C2305, CSOM230C2402 and CSOM230C2413)

At any time during the roll-over, the pasireotide LAR dose may be increased up to a maximum dose of 60 mg per injection if biochemical control is not achieved, i.e. when their GH level \geq 2.5 μ g/L and/or IGF-1 > ULN (age and sex related). Also the pasireotide LAR dose may be reduced if a patient is experiencing a drug related toxicity. The dose should be adjusted in 20 mg steps, e.g. the pasireotide LAR dose can be adjusted from 60 mg to 40 mg or from 40 mg to 20 mg. The decision to change the dose is to be made by the investigator or designee, and the dose change must be recorded in the Dosage Administration Record CRF. Patients should return to the previous dose once the tolerability issue resolves.

Study C2413 specific: The minimum dose to be administered is 10 mg for patients with IGF-1 levels falling below the lower limit of normal and have controlled mean GH levels. The IGF-1 values are required to be confirmed to be below LLN on two consecutive assessments. If biochemical control is maintained, the patient can continue on the lower dose for the remainder of the trial. If biochemical control is lost, the dose should be increased. The 10 mg dose should be obtained from the 20 mg vial.

Table 14-1 Dose modification for AEs, excluding LFT increase, QT prolongation and hyperglycemia

Adverse event	Action
CTCAE grade \leq 2	No drug adjustments

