14.10.2 Treatment interruption and treatment discontinuation

All dose modifications should be based on the worst preceding toxicity.

Each patient is only allowed one dose reduction. In addition, a patient must discontinue treatment with pasireotide LAR if, after treatment is resumed at a lower dose, the toxicity recurs with the same or worse severity

Table 14-12 Criteria for interruption and re-initiation of pasireotide LAR

Recommended dose modifications for pasireotide LAR	
Worst toxicity CTCAE Grade* (value)	Recommended dose modification any time during a cycle of therapy
No toxicity	Maintain dose level
Hematologic	
Neutropenia (ANC)	
Grade 1 (ANC < LLN - 1500/mm ³)	Maintain dose level
Grade 2 (ANC < 1500 - 1000/mm ³)	Maintain dose level
Grade 3 (ANC < 1000 - 500/mm ³)	Omit dose until resolved to ≤ Grade 2, then - If resolved ≤ 7 days, then maintain dose level - If resolved > 7 days, then ↓ 1 dose level

Recommended dose modifications for pasireotide LAR	
Worst toxicity CTCAE Grade* (value)	Recommended dose modification any time during a cycle of therapy
Grade 4 (ANC < 500/mm ³)	Omit dose until resolved to ≤ Grade 2, then - If resolved ≤ 7 days, then maintain dose level - If resolved > 7 days, then ↓ 1 dose level
Thrombocytopenia	
Grade 1 (PLT < LLN - 75,000/mm ³)	Maintain dose level
Grade 2 (PLT < 75,000 - 50,000/mm ³)	Maintain dose level
Grade 3 (PLT < 50,000 - 25,000/mm ³)	Omit dose until resolved to ≤ Grade 1, then - If resolved ≤ 7 days, then maintain dose level - If resolved > 7 days, then ↓ 1 dose level
Grade 4 (PLT < 25,000/mm ³)	Omit dose until resolved to ≤ Grade 1, then ↓ 1 dose level
Febrile neutropenia (ANC < 1.0 x 10 ⁹ /L, fever ≥ 38.5°C)	Omit dose until resolved, then ↓ 1 dose level
Renal	
Serum creatinine	
< 2 x ULN	Maintain dose level
2-3 x ULN	Omit dose until resolved to ≤ Grade 1, then - If resolved ≤ 7 days, then maintain dose level - If resolved > 7 days, then ↓ 1 dose level
Grade 3 (> 3.0 - 6.0 x ULN)	Omit dose and discontinue patient from study treatment
Grade 4 (> 6.0 x ULN)	Omit dose and discontinue patient from study treatment
Hepatic	
Bilirubin	
< 2 x ULN	Maintain dose level
2-3 x ULN	Omit dose until resolved to ≤ Grade 1, then - If resolved ≤ 7 days, then maintain dose level - If resolved > 7 days, then ↓ 1 dose level
Grade 3 (> 3.0 - 10.0 x ULN)	Omit dose until resolved to ≤ Grade 1, then - If resolved ≤ 7 days, then maintain dose level - If resolved > 7 days, then ↓ 1 dose level

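### For SOM230D2101 patients already reduced once, Appendix 4 calls for a further dose reduction at a treated FPG above 250 mg/dL, while Appendix 10 bars it and calls for discontinuation; no text says which governs.

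*Protocol*

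**What the plan says.** Appendix 10 of the protocol governs dose changes for patients rolling over from SOM230D2101. Section 14.10.1 reads: "For each patient, only one dose reduction will be allowed after which the patient should be discontinued from the study". Section 14.10.2 repeats the limit ("Each patient is only allowed one dose reduction") and adds that treatment must stop if "after treatment is resumed at a lower dose, the toxicity recurs with the same or worse severity". The limit is not confined to particular toxicities. The only step named is from 80 mg to 60 mg.

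For hyperglycaemia, the follow-up table in Appendix 10 (Table 14-11) says: "For details on hyperglycemia management, please refer to Appendix 4". Appendix 4 (Section 14.4) then says: "If grade 3 hyperglycemia (FPG >250 mg/dL; >13.9 mmol/L) at any point in the study, despite appropriate anti-diabetic medication, pasireotide dose should be reduced". It puts no ceiling on how often this can happen. Its discontinuation bullet begins "If consistently high glucose values" and covers FPG of at least 240 mg/dL or HbA1c of at least 10% that persists after diabetes management and dose reduction.

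Section 7.1.5.1 uses the same thresholds, under the wording "Uncontrolled diabetes mellitus (DM), consistently high glucose values", but does not mention a prior dose reduction. Section 6.2 names Appendices 2 to 12 together as the dose modification guidelines and does not rank them.

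**The concern.** A SOM230D2101 patient is subject to both appendices. Once the single reduction has been used, the two texts part company on a further treated high glucose value: one asks for a step that the other forbids. Two sites could follow the protocol in good faith and do different things for the same laboratory result.

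What is at stake is mainly continued access. The study exists to keep supplying drug to patients who benefit, and the two instructions differ on whether such a patient stays on it. There is a modest reporting effect as well. SAP Section 7.4.1 tabulates adverse events leading to study drug discontinuation separately from those requiring dose adjustment or interruption, so the table in which an event appears would depend on which text the site followed.

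**Working it through.** The protocol states no figure to reproduce and tests no hypothesis, so the check is a comparison of rules. The thresholds themselves are not the source of the conflict: the paired units agree with each other (240/13.3 = 18.05; 250/13.9 = 17.99).

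The inputs are the cap and recurrence stop (14.10.1, 14.10.2), the reduction and discontinuation bullets (Appendix 4) and the glucose criterion (7.1.5.1). The FPG values 245 and 260 mg/dL are illustrations chosen on either side of 250. Treated means on appropriate anti-diabetic medication.

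| Earlier reductions | FPG (mg/dL) | Treated | Persistent | Appendix 4 | Appendix 10 | Result |
|---|---|---|---|---|---|---|
| 0 | 260 | yes | no | reduce | reduction available | consistent |
| 1 | 245 | yes | no | neither bullet triggered | cap not engaged | consistent |
| 1 | 245 | yes | yes | discontinue | no further reduction available | consistent |
| 1 | 260 | no | no | reduction bullet not triggered | cap not engaged | no second reduction requested |
| 1 | 260 | yes | yes | reduce and discontinue both triggered | discontinue | both reach a stop |
| 1 | 260 | yes | no | reduce again | discontinue | **conflict** |

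The last row, step by step:

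1. FPG is above 250 mg/dL in a treated patient, so Appendix 4 says the dose should be reduced.
2. The value is not persistent, so Appendix 4's discontinuation bullet is not met. The 7.1.5.1 glucose criterion is not met either.
3. One reduction has been used, so 14.10.1 and 14.10.2 allow no second one, and 14.10.1 says the patient should be discontinued. Appendix 10 names no level below 60 mg for a patient who started at 80 mg.
4. If the earlier reduction was itself for hyperglycaemia, the recurrence stop in 14.10.2 may also apply. If it was for a different toxicity, it does not, because it concerns the same toxicity returning. The cap in 14.10.1 applies in both situations. The recurrence stop carries no condition about anti-diabetic treatment, so whether it reaches hyperglycaemia at all also needs stating.

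Next, does any text settle the order? Section 6.2 does not. The adverse-event tables in other appendices (Tables 14-1, 14-5, 14-8, 14-9, 14-10 and 14-13) exclude liver tests, QT prolongation and hyperglycaemia in their titles; Appendix 10 has no such exclusion. Its dose-modification table, 14-12, has a hyperglycaemia row that includes the range above 250 to 500 mg/dL. That row sends the reader to Section 14.2, which in this protocol is the hepatic guidance; the glucose guidance is Section 14.4.

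**The case against.** The strongest reply is that the texts can be read together. Appendix 4 spans all indications and names no dose levels or floors. The parent-specific appendices supply those limits, and Sections 2.3 and 6.1.1 bind dose changes to the parent study's range. On that reading the cap is the boundary within which Appendix 4 operates. This is plausible, but it is not written. The opposite reading, that the specific glucose guidance displaces a general cap, is not written either.

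A second reply is that Appendix 4 is titled as recommended guidance and says the dose should, not must, be reduced. That softens the conflict without removing it: 14.10.1 also says should, and Appendix 10 relies on Appendix 4 for this toxicity.

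Third, Table 14-12 itself sets no dose action for raised glucose, so Appendix 10 does not by itself discontinue a patient for one value of 260 mg/dL under the cap. The stop arises when Appendix 4 asks for a reduction that the cap disallows. That is correct, and it is how the conflict is described here.

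Fourth, reach. Appendix 10 applies only to SOM230D2101, and the SAP tables that derive indication from parent study (Section 4.1, Tables 2-1 and 2-2) list 17 distinct parent studies without it. The tables may be incomplete, but they give no support for saying that the conflict will be met in practice. This stands and limits the weight of the point.

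**Conclusion.** The two appendices conflict in one defined situation: a SOM230D2101 patient with one reduction already used and a single, treated, non-persistent FPG above 250 mg/dL. There are two incompatible instructions and no stated precedence, and the relevant cross-reference in Table 14-12 is wrong. The number of patients affected cannot be derived from the documents and may be zero.

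Stronger readings are not supported:

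- A reader might count three outcomes by adding continuation under Section 7.1.5.1. That section lists reasons to stop; not meeting one of them is not an instruction to continue unchanged.
- A reader might take Appendix 4 to require reduction at every value above 250 mg/dL, or to allow a stop solely for persistent values. The reduction is conditional on anti-diabetic treatment, and the stop rule is not described as exclusive.
- A reader might size the problem from the hyperglycaemia rates of 49% and 47% in Section 1.2.1.2.2. Those are all hyperglycaemia events in Cushing's disease, not values above 250 mg/dL after a dose reduction in neuroendocrine tumour patients.
- A reader might expect SAP deviations D03 and S04 to be scored wrongly. D03 follows the hyperglycaemia discontinuation criteria of 7.1.5.1, and S04 is worded against the parent protocol. Neither depends on Appendix 4.
- The adverse-event tables would still report correctly the action taken, since Section 8.1.1 records it as it happened. What would vary is the action.

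**What to change.** Reconcile Sections 14.10.1 and 14.10.2 with Appendix 4 and Section 7.1.5.1. The text should state:

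- whether a reduction made for hyperglycaemia counts towards the one allowed reduction, and whether the cap applies to hyperglycaemia at all;
- whether the recurrence stop applies to hyperglycaemia;
- which text governs when the one reduction has already been used.

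The choice of rule belongs to the clinical team, and none is proposed here. The hyperglycaemia row of Table 14-12 should be pointed at the glucose guidance rather than Section 14.2. The sponsor should also confirm whether any SOM230D2101 patient enrolled; if so, the study is missing from the SAP's parent-study tables.

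The cost is a sentence or two in Appendix 10, a matching cross-reference in Appendix 4 and one corrected pointer. No added data collection or analysis is needed.

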14.10.2 Treatment interruption and treatment discontinuation

All dose modifications should be based on the worst preceding toxicity.

Each patient is only allowed one dose reduction. In addition, a patient must discontinue treatment with pasireotide LAR if, after treatment is resumed at a lower dose, the toxicity recurs with the same or worse severity

Table 14-12 Criteria for interruption and re-initiation of pasireotide LAR

Recommended dose modifications for pasireotide LAR	
Worst toxicity CTCAE Grade* (value)	Recommended dose modification any time during a cycle of therapy
No toxicity	Maintain dose level
Hematologic	
Neutropenia (ANC)	
Grade 1 (ANC < LLN - 1500/mm ³)	Maintain dose level
Grade 2 (ANC < 1500 - 1000/mm ³)	Maintain dose level
Grade 3 (ANC < 1000 - 500/mm ³)	Omit dose until resolved to ≤ Grade 2, then - If resolved ≤ 7 days, then maintain dose level - If resolved > 7 days, then ↓ 1 dose level

Recommended dose modifications for pasireotide LAR	
Worst toxicity CTCAE Grade* (value)	Recommended dose modification any time during a cycle of therapy
Grade 4 (ANC < 500/mm ³)	Omit dose until resolved to ≤ Grade 2, then - If resolved ≤ 7 days, then maintain dose level - If resolved > 7 days, then ↓ 1 dose level
Thrombocytopenia	
Grade 1 (PLT < LLN - 75,000/mm ³)	Maintain dose level
Grade 2 (PLT < 75,000 - 50,000/mm ³)	Maintain dose level
Grade 3 (PLT < 50,000 - 25,000/mm ³)	Omit dose until resolved to ≤ Grade 1, then - If resolved ≤ 7 days, then maintain dose level - If resolved > 7 days, then ↓ 1 dose level
Grade 4 (PLT < 25,000/mm ³)	Omit dose until resolved to ≤ Grade 1, then ↓ 1 dose level
Febrile neutropenia (ANC < 1.0 x 10 ⁹ /L, fever ≥ 38.5°C)	Omit dose until resolved, then ↓ 1 dose level
Renal	
Serum creatinine	
< 2 x ULN	Maintain dose level
2-3 x ULN	Omit dose until resolved to ≤ Grade 1, then - If resolved ≤ 7 days, then maintain dose level - If resolved > 7 days, then ↓ 1 dose level
Grade 3 (> 3.0 - 6.0 x ULN)	Omit dose and discontinue patient from study treatment
Grade 4 (> 6.0 x ULN)	Omit dose and discontinue patient from study treatment
Hepatic	
Bilirubin	
< 2 x ULN	Maintain dose level
2-3 x ULN	Omit dose until resolved to ≤ Grade 1, then - If resolved ≤ 7 days, then maintain dose level - If resolved > 7 days, then ↓ 1 dose level
Grade 3 (> 3.0 - 10.0 x ULN)	Omit dose until resolved to ≤ Grade 1, then - If resolved ≤ 7 days, then maintain dose level - If resolved > 7 days, then ↓ 1 dose level
Grade 4 (> 10.0 x ULN)	Omit dose and discontinue patient from study treatment NOTE: If grade 3 or 4 hyperbilirubinemia is due to the indirect (unconjugated) component only, and hemolysis as the etiology has been ruled out as per institutional guidelines (e.g. review of peripheral blood smear and haptoglobin determination), then ↓ 1 dose level and continue treatment at the discretion of the investigator
AST or ALT	
Grade 1 (> ULN - 2.5 x ULN)	Maintain dose level
Grade 2 (> 2.5 - 5.0 x ULN)	Maintain dose level

Recommended dose modifications for pasireotide LAR	
Worst toxicity CTCAE Grade* (value)	Recommended dose modification any time during a cycle of therapy
(>5.0 and ≤ 8 x ULN)	If ALT or AST return to less than 5 x ULN study drug can be resumed and patient can continue study per protocol. If persistent for more than 14 days, discontinue patient from study treatment. In the event of a re-occurrence, discontinue patient from study treatment.
(> 8 x ULN)	Omit dose and discontinue patient from study treatment
Pancreatic	
Pancreatitis	
Grade 1	Maintain dose level
Grade 2	Maintain dose level
Grade 3	Omit dose and discontinue patient from study treatment
Grade 4	Omit dose and discontinue patient from study treatment
Amylase and/or lipase	
Grade 1 (> ULN - 1.5 x ULN)	Maintain dose level
Grade 2 (> 1.5 - 2.0 x ULN)	Maintain dose level
Grade 3 (> 2.0 - 5.0 x ULN)	For asymptomatic: Omit dose until resolved to ≤ Grade 1, then - If resolved ≤ 7 days, then maintain dose level - If resolved > 7 days, then ↓ 1 dose level For symptomatic: Omit dose and discontinue patient from study treatment Omit dose and discontinue patient from study treatment A CT scan or other imaging study to assess the pancreas, liver and gallbladder must be performed within 1 week of the first occurrence of any ≥ CTCAE grade 3 of amylase and/or lipase.
Grade 4 (> 5.0 x ULN)	
Endocrine/metabolic	
Fasting plasma glucose (FPS) or 2-hour postprandial capillary glucose (PPG)	
FPG <126 mg/dL or PPG < 140 mg/dL	Maintain dose level
Grade 1 (> ULN – 160 mg/dL)	Please refer to Appendix 14.2 'Guideline for study drug-induced hyperglycemia'
Grade 2 (> 160 – 250 mg/dL)	
Grade 3 (> 250 – 500 mg/dL)	
Grade 5 (> 500 mg/dL)	
Cardiac	
Cardiac - prolonged QTc interval	
- QTcF > 480 ms and ≤ 500 ms	If at any time a QTcF > 480 ms and ≤ 500 ms is observed a cardiology consultation must be sought to re-evaluate the abnormal ECG finding.

Recommended dose modifications for pasireotide LAR	
Worst toxicity CTCAE Grade* (value)	Recommended dose modification any time during a cycle of therapy
- QTcF > 500 msec	
 1. Triplicate ECGs (2-3 minutes apart) need to be taken approximately 1 hour after the initial ECG. 2. If the mean QTcF is > 500 ms, the patient must postpone study treatment until a cardiologist has re-evaluated the ECG. 3. The re-evaluation of ECG needs to be done as soon as practical but within 7 days of the initial abnormal ECG. 4. If the cardiologist confirms a mean QTcF > 500 ms, the patient must be discontinued.
Cardiac general Grade 1 or 2 Grade 3 Grade 4	
Maintain dose level
 
Omit dose until resolved to ≤ Grade 1, then ↓ 1 dose level
 
Omit dose and discontinue patient from study treatment

Other adverse events	
Grade 1 or 2 Grade 3 Grade 4	
Maintain dose level
 
Omit dose until resolved to ≤ Grade 1, then ↓ 1 dose level
 
Omit dose and discontinue patient from study treatment

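### Appendix 10 gives re-treatment recovery grades that differ by one grade between Tables 14-11 and 14-12, in opposite directions, for neutropenia and for amylase/lipase

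*Protocol*

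**What the plan says.** The appendix is headed "Dose modification information for patients with neuroendocrine tumors receiving pasireotide LAR (from protocol SOM230D2101"), and Protocol Section 6.2 sends investigators to the appendices for dose modification.

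**Neutropenia.** For grade 3 or higher, Table 14-11 requires repeat testing until the value is no worse than "CTCAE grade 1 to allow for initiation of re-treatment, and then at least weekly until either initiation of retreatment or until stabilization". For both grade 3 and grade 4, Table 14-12 says "Omit dose until resolved to ≤ Grade 2, then" keeps the same dose if recovery took 7 days or less, with one dose level lower if recovery took more than 7 days.

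**Amylase/lipase.** For grade 3 or higher, Table 14-11 requires repeat testing until the value is no worse than "CTCAE grade 2 to allow for initiation of re-treatment, and then at least weekly until either resolution to" grade 1 or lower, or stabilization. It makes no distinction by symptoms. For grade 3, Table 14-12 says "For asymptomatic: Omit dose until resolved to ≤ Grade 1, then" applies the same 7-day rule. Its other branch reads "For symptomatic: Omit dose and discontinue patient from study treatment".

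**Linked rules.** Section 14.10.1 requires discontinuation "If a patient requires a dose delay of > 21 days from the intended day of the next scheduled dose of pasireotide LAR". Sections 14.10.1 and 14.10.2 allow each patient one dose reduction only. No sentence says which table prevails where they differ.

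**The concern.** An investigator deciding whether to give the next injection finds two recovery grades in one appendix. Because the mismatch runs in opposite directions, neither table is consistently the stricter: Table 14-11 is stricter for neutropenia and Table 14-12 for amylase/lipase. Two sites could therefore treat the same laboratory course differently, and each could point to the protocol.

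The recovery grade governs more than timing. In Table 14-12 it is the point at which the 7-day rule for keeping or lowering the dose is judged, and a lowered dose uses up the only reduction allowed. A longer hold also brings the patient closer to the mandatory 21-day discontinuation.

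Any such case would enter the SAP's summaries of dose interruption and reduction (Section 7.3) and of AEs leading to discontinuation or requiring dose adjustment or interruption (Section 7.4.1). Those counts would then partly reflect which table a site followed.

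**Working it through.** No sample-size or power figure is involved. The check sets the two tables side by side and traces patients through them.

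| Toxicity | Table 14-11: re-treat at | Table 14-12: restart at | Agree? |
|---|---|---|---|
| Neutropenia, grade 3 or 4 | grade 1 or lower | grade 2 or lower | No; 14-11 stricter by one grade |
| Amylase/lipase, grade 3, asymptomatic | grade 2 or lower | grade 1 or lower | No; 14-12 stricter by one grade |
| Amylase/lipase, grade 3, symptomatic | grade 2 or lower (no split by symptoms) | not restarted; discontinue | No |
| Thrombocytopenia, grade 3 or 4 | grade 1 or lower | grade 1 or lower | Yes |
| Creatinine 2-3 x ULN | grade 1 or lower, or baseline | grade 1 or lower | Yes on the grade |

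The grade 4 amylase/lipase cell of Table 14-12 is displaced in the text available, so nothing here rests on it.

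**Disputed bands.** By the limits printed in Table 14-12, grade 2 means ANC below 1500 down to 1000/mm3, and amylase/lipase above 1.5 and up to 2.0 x ULN.

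**Day count.** Pasireotide LAR is given every 28 days, and the 21-day limit runs from the intended dosing day, not from onset of toxicity. In the examples, day 0 is the day an injection is due and also the day the abnormal value is found. The laboratory values are illustrative assumptions. A delay first exceeds 21 days on day 22.

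*Example 1: neutropenia.* ANC is 800/mm3 on day 0 (grade 3) and 1200/mm3 from day 5 (grade 2).
- Table 14-12: restart on day 5. Since 5 ≤ 7, the dose is unchanged. Had grade 2 been reached only on day 10, then 10 > 7 and the dose would drop one level.
- Table 14-11: grade 1 is not reached, so the patient is held. That table prescribes nothing further. If ANC is still 1200/mm3 on day 22, Section 14.10.1 requires discontinuation.

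*Example 2: asymptomatic lipase.* Lipase is 3 x ULN on day 0 (grade 3) and 1.8 x ULN from day 5 (grade 2).
- Table 14-11: re-treatment is allowed from day 5.
- Table 14-12: the dose stays omitted. If grade 1 is reached on day 10, then 10 > 7 and the dose drops one level. If lipase is still 1.8 x ULN on day 22, Section 14.10.1 requires discontinuation.

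*Example 3: symptomatic lipase.* With the same values, Table 14-11 allows re-treatment on day 5 and Table 14-12 discontinues the patient.

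*Where the recovery grades do not clash.* Suppose ANC is 800/mm3 on day 10 of a 28-day cycle. No injection is due for another 28 - 10 = 18 days. If ANC has reached grade 1 by then, both recovery thresholds are met. The same holds for asymptomatic grade 3 amylase/lipase.

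**The case against.** The strongest reply is that the tables have different jobs. Table 14-11 is titled and introduced as follow-up, and its instructions are test frequencies. Table 14-12 is titled as the criteria for stopping and restarting the drug. On that reading a site would use Table 14-12 for dosing.

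This makes Table 14-12 the more natural place to look, but it does not remove the conflict. Table 14-11 expressly names the grade that permits re-treatment. The parallel Table 14-6 in Appendix 7 uses the same hematology and pancreatic recovery grades for monitoring without tying them to re-treatment, so a monitoring-only form exists in this protocol and Table 14-11 departs from it. Section 14.10.1 also blurs the division by sending follow-up to Table 14-12.

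A second reply is that Table 14-12 is headed as recommendations and Section 6.2 leaves dose changes to the investigator's judgment. That softens the dose-level steps. The 21-day and one-reduction rules are mandatory all the same.

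A reader might also infer more than the documents support:
- *That both toxicities lead to hold, reduction or discontinuation under the stricter table.* This is true of asymptomatic amylase/lipase under Table 14-12 with Section 14.10.1. For neutropenia, Table 14-11 gives only a hold. Discontinuation comes only through the 21-day rule, and the reduction step exists only in Table 14-12.
- *That there are two competing 7-day clocks.* Only Table 14-12 has one.
- *That Section 14.10.1 sets a third threshold.* Its endpoint of grade 1 or baseline is for following the toxicity. It is compatible with re-dosing earlier under either table.
- *That D-coded protocol deviations are affected.* In SAP Attachment 8.1, D01 to D05 concern hepatic, QT and hyperglycemia criteria, pregnancy and loss of benefit, not these toxicities.

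**Conclusion.** The inconsistency stands in the current protocol text. For neutropenia and for asymptomatic grade 3 amylase/lipase, the stated re-treatment grades differ by one grade in opposite directions. For symptomatic grade 3 amylase/lipase, one table permits re-treatment and the other ends treatment.

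The reach is narrow: patients at grade 2 but not grade 1 when an injection is due, and patients with symptomatic grade 3 amylase/lipase. Within that group the choice of table can decide whether a dose is given and, if the value persists, whether the patient stays in the study.

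A reader might infer that reported trial results are distorted. The documents do not show this. SOM230D2101 is not among the parent studies mapped in SAP Tables 2-1 and 2-2, so either no such patient enrolled or the mapping is incomplete. The number affected is unknown and may be zero. That limits the practical effect but not the contradiction, because the protocol still issues both instructions. The correction is worth making if any such patient is enrolled. No view is taken here on which recovery grade is right.

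**What to change.** Reconcile Tables 14-11 and 14-12 so that neutropenia and amylase/lipase each have one re-treatment recovery grade, stated in one table only, and so that symptomatic grade 3 amylase/lipase has one stated course. Limit the other table to monitoring frequency for these rows, with a cross-reference for the re-treatment grade. Table 14-6 shows wording confined to monitoring. The sponsor's medical team must decide the thresholds.

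The sponsor should first check, from the parent-study field that SAP Section 4.1 uses to derive indication, whether any SOM230D2101 patient is enrolled. If none is, a recorded clarification is enough. If any is, the change is a text correction to one appendix, made by amendment as Protocol Section 12.1 requires, with no added procedures or data collection.
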